6.7 BASELINE, TIME WINDOWS AND CALCULATED VISITS

Study days and visits will be labelled according to the flow chart of the CTP.

Unless otherwise specified, baseline is defined as the latest time-point before the very first treatment administration (\leq 7 days before first administration). If this criterion is not fulfilled then no baseline will be derived.

For height baseline is defined as the latest time point before the very first treatment administration (no 7-day-rule).

ECOG:

Baseline is defined as value at the day of first administration. If there is no value available at the day of first admin, the latest value before the first admin will be used.

Laboratory values/ other safety measurements:

Baseline is defined as value at time point closest to but prior to first administration of trial medication of the first course. (i.e. Time of laboratory value on day of first administration \leq time of first administration, then lab value on day of first administration = lab value at baseline. If time of lab value on day of first administration $>$ time of first administration then closest non-missing lab value before time of first admin = lab at baseline)

If any of these times are missing and date of lab = date of first admin, then lab at first admin = lab at baseline.

ECG

Baseline ECG is available from three time points (prior infusion at course 1 visit 1, course 1 visit 4 and course 2 visit 1). To account for possible variations between the study days, two different baseline definitions will be used:

1. Individual baseline is defined as the mean of the triplicate at the time point closest to but prior to the start of the infusion at each time point, i.e. each time point has its own baseline.

2. Combined baseline is defined as the mean of the (three) triplicates at the time points closest to but prior to the start of the infusion at the three time points, i.e. a common baseline is used.

Day 1 will be the day of randomisation, so time to event will be taken from Day 1.

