The non-clinical safety profile of BI 6727 is considered favourable regarding the oncological indication and the antiproliferative principle. In 3-cycle toxicity studies in dogs and rats mechanism-related side effects were observed in organs with high turnover as expected. Main target organs were the gastrointestinal tract (mucosal lesions), bone marrow and lymphatic system. Complete reversibility even of severe lesions at higher doses was observed. Moreover, no evidence for unspecific toxicity affecting other organs such as kidney or liver was found. However, an exploratory investigation on the cardiovascular system in pigs, given at very high doses of up to 30 mg/kg BI 6727, showed that BI 6727 induced QT prolongation starting at a plasma level of 3700 nmol/L and slight QTcSE prolongation in chronically treated dogs starting at 36 mg/m² at plasma levels of about 880 – 1090 nmol/L. The hERG channel was inhibited with an IC₅₀ value of 2.4 µmol/L while the action potential in guinea pig papillary muscle was not affected up to 10 µmol/L. Based on these results, QT-monitoring is continued in the clinical phase II trials with BI 6727. More detailed information is provided in the Investigator's Brochure (IB; [c01694302-14](#)).

To date 50 patients with a variety of tumour types have been treated in a phase I trial with BI 6727. Thirty-one patients were treated at doses at or above 300 mg, with the maximum tolerated dose (MTD) at 400 mg. The results demonstrated that BI 6727 had good tolerability with reversible haematotoxicity (neutropenia, thrombocytopenia) constituting the dose limiting toxicity. No relevant unspecific toxicity has been observed as yet. Encouraging signs of efficacy were seen in two patients with confirmed partial regressions of urothelial and

ovarian tumours, respectively. In addition long term disease stabilizations were observed in several patients. More than 20 courses of treatment were given without signs of persisting or cumulative toxicity.

In the electrocardiogram (ECG) monitoring BI 6727 dose dependant QtcF prolongations at the time of C_{max} have been observed in patients, but no associated clinical events were reported.

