4.1.1 Identity of investigational products

4.1.1.1 BI 6727

Substance (INN):	BI 6727
Pharmaceutical form:	Solution for infusion after dilution
Source:	Boehringer Ingelheim Pharma GmbH & Co. KG
Unit strength:	2 mg /mL (vials with 100 mL) OR 2 mg/mL (vials with 175 mL)
Daily dose:	See section 4.1.3
Duration of use:	Single dose on day 1 and 15 of each 28 day cycle
Route of administration:	intravenous
Posology:	Infusion over 60 minutes

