5.2.7 ECG

12-lead resting ECG will be performed in all patients at the screening visit and at the EoT visit.

For patients in treatment schedules A and B ECGs will be recorded with every infusion of BI 6727 (before the start and immediately before the end of the BI 6727 infusion), additional ECGs will be recorded in cycle 1. In cycle 1 at visit 1 and 4, and at visit 1 in cycle 2 the ECGs must be performed at the related PK sampling time points. All ECGs have to be digitally recorded using dedicated equipment provided by a contract research organisation (CRO; [REDACTED]) at the following time points:

After approval of Protocol Revision I, ECGs should be recorded prior to and at the end of volasertib infusions. No digital and triplicate recording is required anymore. ECGs can be recorded with a local ECG machine.

- Visit 1 (day 1) of cycle 1
 - ! prior to start of infusion of BI 6727
 - ! immediately before the end of infusion of BI 6727 (1:00 hour). The infusion should not be finished yet at that sampling time point.
 - ! 2 hours after the start of infusion;
 - ! 4 -6 hours after the start of infusion
 - ! 24 hours after the start of the infusion
- Visit 4 (day 15) of cycle 1
 - ! prior to start of infusion of BI 6727

- ! immediately before the end of infusion of BI 6727 (1:00 hour). The infusion should not be finished yet at that sampling time point.
- ! 2 hours after the start of infusion;
- ! 4 -6 hours after the start of infusion

- Visit 1 (day 1) and visit 4 (day 15) of every cycle \geq 2:

- ! prior to start of infusion of BI 6727
- ! immediately before the end of infusion of BI 6727 (1:00 hour). The infusion should not be finished yet at that sampling time point.

The recording will be checked for pathological results (to be recorded as AEs) by the investigator. In addition, a centralized evaluation of all 12-lead ECGs recorded will be performed by a CRO (████████).

After approval of Protocol Revision I, transmissions for central ECG analysis will be discontinued.

In addition, ECGs should be done whenever the investigator deems necessary.

In case of drug related ECG changes, additional ECG monitoring will be performed in the respective and later cycles of treatment.

In case of QTcF > 470 ms prior to the planned start of infusion of BI 6727, the trial drug should not be administered.

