6.2.1 Screening and run-in phase

6.2.1.1 Screening Visit

The screening phase, i.e. the phase after informed consent and before the very first administration of the trial drug, may be as long as 14 days.

The following will be obtained and / or performed:

- ! Informed consent
- ! Demographics (sex, birth date, race)
- ! Medical history (oncological and relevant non-oncological)
- ! Review of inclusion and exclusion criteria (patient eligibility)
- ! Documentation of reasons why the patient is considered ineligible for intensive treatment
- ! Resting 12 lead-ECG (digital, triplicate)
- ! Blood sample for pharmacogenetic investigations (optional, only after signed separate informed consent)
- ! Physical examination, body height, weight, vital signs and ECOG performance score
- ! Concomitant therapy
- ! Safety laboratory, including coagulation parameters and urinalysis (see section 5.2.5)

- ! Serum pregnancy test for women of childbearing potential
- ! Disease assessment: peripheral blood and bone marrow evaluation for leukaemia, pharmacodynamics (FACS and cytospins see section 5.6), AML cytogenetics and molecular genetics (see section 5.3.4). Bone marrow aspiration performed before inclusion in the trial may be accepted as baseline assessment if done within fourteen days before first treatment administration
If applicable imaging (or other appropriate means of assessment) of extramedullary manifestation of leukaemia.
- ! Assignment / Randomisation

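### SAP 6.7 plans no patient-level QTcF change from the pre-dose course 1 visit 1 ECG after that visit; add it as a third reference beside the two planned baselines

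*SAP*

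**What the plan says.** SAP 6.7 has a general rule that baseline is the last value before the very first administration, unless another rule is given. ECG has its own rule: "Baseline ECG is available from three time points (prior infusion at course 1 visit 1, course 1 visit 4 and course 2 visit 1"). The reason stated is "To account for possible variations between the study days, two different baseline definitions will be used".

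- **Individual baseline:** the mean of the triplicate before that day's infusion, "at each time point, i.e. each time point has its own baseline".
- **Combined baseline:** "Combined baseline is defined as the mean of the (three) triplicates at the time points closest to but prior to the start" of infusion on the three days, used as a common reference.

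SAP 5.2.5 plans QTcF change at each time point, absolute QTcF, and categories of the maximum increase (up to 30, over 30 to 60, over 60 ms). SAP 7.7.4.2 plans summaries of change and shift tables. Neither section names the baseline to be used.

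Protocol 4.1.1.1 gives the BI 6727 dosing: "Single dose on day 1 and 15 of each 28 day cycle". Protocol 2.3 lists QTc change during and after the infusion as a secondary endpoint. Protocol 1.2.1 reports one clinical ECG signal: "BI 6727 dose dependant QtcF prolongations at the time of" Cmax.

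**The concern.** The course 1 visit 4 pre-infusion triplicate follows one BI 6727 infusion, and the course 2 visit 1 triplicate follows two. The individual baseline uses these ECGs as the reference at those visits. The combined baseline takes two of its three triplicates from them at every visit, so even course 1 visit 1 changes are measured partly against ECGs recorded after exposure.

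A shift that is still present before the next infusion would therefore be taken out, in whole or in part, of the planned change values and of the over 30 and over 60 ms categories. In the same section, ECOG, laboratory and other safety measurements are referred back to first administration. The reason given for treating ECG differently is between-day variation, which does not address a persisting shift.

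**Working it through.** **ECGs covered.** Protocol 5.2.7 schedules these post-start ECGs up to course 2 visit 1:

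- course 1 visit 1: four (end of infusion, 2 h, 4–6 h, 24 h)
- course 1 visit 4: three
- course 2 visit 1: one

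Of these eight, the four at course 1 visit 1 get a change from the course 1 visit 1 triplicate, through the individual baseline. None of the other four does. Protocol 5.2.7 also records ECGs at "Visit 1 (day 1) and visit 4 (day 15) of every cycle" from cycle 2 on. Course 2 visit 4 and later visits are not among the three time points in SAP 6.7.

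**Algebra.** Let s4 and s2 be the pre-infusion shifts at course 1 visit 4 and course 2 visit 1, measured from course 1 visit 1. Relative to a change from course 1 visit 1:

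- the individual baseline subtracts s4 at course 1 visit 4 and s2 at course 2 visit 1
- the combined baseline subtracts (0 + s4 + s2)/3 at every visit

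With s4 = s2 = r the combined term is 2r/3. If course 2 visit 1 is missing and the other two triplicates are averaged, it is r/2; SAP 6.7 does not say what is done. Changes are understated if r > 0, overstated if r < 0 and unaffected if r = 0.

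Example: a course 1 visit 4 ECG lies 65 ms above course 1 visit 1 and r = 10. The individual change is 65 − 10 = 55 ms. The combined change is 65 − 6.7 = 58.3 ms. Both fall below the 60 ms cut.

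**Illustrative size.** The documents state no figure to reproduce and give no r, so every input here is assumed. There are three visits, the acute rise e is N(30, 15) ms and constant within patient, and the category is set by the maximum change. Without noise the maximum is e + b:

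- course 1 visit 1 reference: b = max(r, 0)
- individual: b = 0
- combined: b = max(−2r/3, r/3)

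The share above 60 ms is 1 − Φ((30 − b)/15).

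| r (ms) | Course 1 visit 1 | Individual | Combined |
|---|---|---|---|
| −6 | 2.3% | 2.3% | 4.2% |
| 0 | 2.3% | 2.3% | 2.3% |
| 3 | 3.6% | 2.3% | 2.7% |
| 6 | 5.5% | 2.3% | 3.1% |
| 12 | 11.5% | 2.3% | 4.2% |

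**Cost of a single-day reference.** Add independent between-day noise d1, d2, d3 with SD s. The course 1 visit 1 maximum becomes e + max(0, r + d2 − d1, r + d3 − d1). At r = 0 and s = 5 / 8 / 10 ms, the share above 60 ms is 5.1 / 8.5 / 11.4% by simulation (5.15 / 8.56 / 11.46% by numerical integration), against 2.3% without noise. The combined shares are 4.5 / 6.7 / 8.6%.

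**Mean shift.** Independent noise does not bias the mean pre-infusion shift. With 43 patients (the planned phase IIa number per schedule, assumed to have both ECGs), the 95% half-width is 1.96 × s × √(2/43) = 2.1 / 3.4 / 4.2 ms for s = 5 / 8 / 10. SAP 7.7.4.2 summarises MTD groups that include phase II patients, so the actual number will differ.

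**The case against.** The strongest case is that the endpoint is the effect during and after infusion and the only clinical signal described is at Cmax. A same-day baseline suits both, so a third baseline is a preference. This stands as a reason to keep the individual baseline. It does not explain a combined baseline made mostly of post-exposure ECGs.

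Second, a reader might infer that the plan cannot show a persisting shift at all. The documents do not support that. Absolute QTcF is planned at each time point. In patients with all three triplicates, the mean shift also follows from the two planned baselines. Individual minus combined change is (s4 + s2)/3 at course 1 visit 1 and (s4 + s2)/3 − s4 at course 1 visit 4, and these differ by exactly s4. What the planned tables do not give is each patient's change from the drug-free ECG.

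Third, a maximum-based table against one day's ECG can mislead. No shift with 8 ms noise gives 8.5% above 60 ms, more than a true 6 ms shift without noise (5.5%). This stands and limits the fix. Nor may a reader assume that the individual and course 1 visit 1 tables bracket the true share. With 5 ms of within-day noise on each triplicate mean and r = 6, the individual share is 6.6% and the course 1 visit 1 share about 10 to 20% (between-day SD 0 to 10 ms). Both exceed 5.5%.

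Fourth, SAP 6.4 and section 9 are not in the available text, so a further definition there cannot be excluded. For visits after course 2 visit 1, the general pre-first-dose default could be argued to apply. For the three listed visits it gives way to the ECG rule.

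**Conclusion.** The point holds as a limited gap. For ECGs after course 1 visit 1, the plan gives no patient-level change from the only pre-infusion triplicate that precedes all BI 6727. A persisting shift r would be removed in full by the individual baseline at later visits and by 2r/3 by the combined baseline at every visit.

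It would go too far to conclude that the planned QTc analysis is biased or hides prolongation. The documents give no r, and r may be zero or negative. Absolute QTcF and its 450, 470 and 500 ms categories are unaffected. The percentages above only illustrate the mechanism under assumed inputs. The analysis is descriptive, and the change is optional.

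**What to change.** In SAP 6.7, add the course 1 visit 1 pre-infusion triplicate as a third ECG reference. Then:

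1. Tabulate the pre-infusion QTcF shift from it at course 1 visit 4 and course 2 visit 1 (N, mean, 95% CI).
2. Summarise QTcF, QTcB and QT change by visit against it, beside the individual and combined baselines.
3. Name the baseline used in every ECG change, category and shift table.
4. Keep the individual baseline for the acute infusion effect.
5. Treat any over 30 or over 60 ms categories against course 1 visit 1 as supplementary, with a note that between-day noise raises maximum-based shares even when r = 0.

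The cost is SAP wording, programming and one more set of tables; the ECGs are already recorded. The drawback is that a single-day reference is noisier, so it should supplement the planned baselines and not replace them.

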6.8 GENERAL CALCULATION RULES

Months = days / 30, Years = days / 365.25 = months / 12

In the case of having multiple values at one visit, for example, laboratory data or vital signs, then the worst case will be used, for post baseline values. Note that pre-treatment values are handled under 'baseline'. To determine worst case, in the case of laboratory data, [section 5.2.2](#) indicates the worst case. In the case of vital signs, the minimum value will be used for weight and the maximum value for ECOG.

7. PLANNED ANALYSIS

For in-text tables, the set of summary statistics is: N (number of patients with non-missing values), mean, standard deviation (SD).

For end-of-text tables, the set of summary statistics is: N / Mean / SD / Min / Median / Max.

For appendix tables, the set of summary statistics is: N / Mean / SD / Min / Q1 (lower quartile) / Median / Q3 (upper quartile) / Max.

Tabulations of frequencies for categorical data will include all possible categories and will display the number of observations in a category as well as the percentage (%) relative to the respective treatment group. Percentages will be rounded to one decimal place. The category missing will be displayed if and only if there are actually missing values. Percentages will be based on all patients in the respective patient set whether they have non-missing values or not.

In general all analyses will be performed for the treated set (phase I) and the treated set (phase II) separately. No pooling across these two treated sets will be performed unless noted otherwise.

7.1 DEMOGRAPHIC AND OTHER BASELINE CHARACTERISTICS

Standard descriptive analysis and summary tables will be presented for all patients of the treated set by treatment group. At the report planning meeting it will be decided which additional variables will be tabulated in chapter 15 or the interim section of the CTR.

Disposition of patients

Standard descriptive analysis of the disposition will be provided.

If applicable, the number of patients who will continue treatment after database lock will be reported in the disposition table, separately.

Additionally, patients with discontinuations of the trial medication due to DLT will be listed by treatment and the reasons will be given. Listing of all patients with dose changes will be provided.

Important protocol violation

A table or listing of patients with protocol violations will be created.

Demographics and baseline characteristics

Standard descriptive analysis of the disposition will be provided.

7.2 CONCOMITANT DISEASES AND MEDICATION

Only descriptive statistics are planned for this section of the report.

A summary of the most frequently concomitant medication (drug classes and generic Name for patients with medication at generic Name) during the treatment and before starting of treatment will be reported. Separate listings/tables will be provided for therapy starting before therapy and those therapies starting after first administration of the trial drug. A summary of the most frequently concomitant diseases (system organ class (SOC) and PT) will be reported. A summary of concomitant therapy will be given.

Listings of the data will present the concomitant therapy PT and verbatim text as well as the verbatim text of the indication. In addition the listings will include study day for start and stop dates and duration of therapy. Patients with no concomitant therapy will not be included in the listing. The number of these patients will be presented by a footnote.

7.3 TREATMENT COMPLIANCE

Only descriptive statistics of the variable "all administration according to the protocol" are planned for this section of the report. "all administration according to the protocol" equals 'no' if any of the entries for 'Administration according to protocol' equals 'no'. Otherwise it is 'yes'. The variable will be derived separately for BI 6727 and cytarabine if applicable.

For patients with "all administration according to the protocol" equals 'no' a listing will be presented.

7.4 PRIMARY ENDPOINTS

One primary objective for this study is the tolerability and safety of the BI 6727 in each treatment schedule as reflected by the MTD (phase I part). Refer to section [7.7](#) for a description of the analysis of safety and tolerability.

The primary endpoint for efficacy in the phase II part is objective response derived from the data of all courses. The primary analysis of efficacy will be done for all patients of the treated set (phase II) for both treatment schedules separately. Patients with objective response will be listed (both phase I and phase II).

7.4.1 Statistical Group Comparisons

All statistical group comparisons will be performed with respect to the treated set (phase II). The comparison of the treatment schedule to the control schedule will be based on the conditional power approach and on a stopping for futility check [[7,8.](#)]. The conditional power for showing superiority of a treatment schedule with respect to the control schedule at a later time point will be evaluated assuming that the final analysis is the interim analysis of a larger trial. These calculations will be based on an O'Brien-Fleming design with interim analysis to stop for futility. The assumptions are an information fraction of 60% of patients, an overall type I error of 5% (one-sided), 15% objective response rate in the control vs. 30% objective response rate in experimental arm and a power of 65% as described in the CTP. The

conditional power will be computed under the current trend hypothesis [8.] using the standardized logarithm of the odd's ratio of proportions as a test statistic (approximately $N(0,1)$ distributed). [REDACTED] will be used for these computations.

Additionally, similar computations will be performed for other scenarios with a planned sample size of approximately 86 patients at the assumed interim analysis (25% information fraction, alpha=0.025 and power 90%, 33% information fraction, alpha=0.025 and power 80% as well as 40% information fraction, alpha=0.05 and power 80%).

The conditional power will be evaluated in addition under the null hypothesis of no treatment effect and under the assumption that the true treatment effect (measured as the log odds ratio) captures only 50% of the observed treatment effect in order to check the robustness of the result.

Odds ratios, confidence intervals, and Fisher's exact test will be used to compare treatments in an exploratory manner if appropriate.

Additionally, objective response rates will be evaluated by a Bayesian approach with a non-informative prior (9.) given by a beta(1,1) distribution. Denoting the total number of patients per arm by n and the number of responders per arm by r this leads to a beta($1+r, 1+n-r$) distribution for the posterior (per arm separately).

Based on this approach the following posterior probabilities will be evaluated: Probability that the treatment arm is at least as good as the control arm, probability that the treatment arm is at least 5% better than the control arm, probability that the treatment arm is at least 10% better than the control arm. Evaluation is performed based on simulating the posterior distribution for each arm $m=1000000$ times and by evaluating the respective characteristics.

The exploratory nature of these analyses will be considered when interpreting the significance levels. P-values derived from statistical tests smaller than 5% will only be reported as nominally significant regarding the small sample size in each treatment schedule.

For the genetic subgroups defined in [Section 6.4](#) frequency tables of best overall response will be presented.

